2 STUDY OBJECTIVES AND ENDPOINTS

OBJECTIVES	ENDPOINTS
Primary	Efficacy endpoint:
To evaluate the efficacy of ASN002 in subjects with moderate to severe chronic hand eczema (CHE) based on hand modified Total Lesion Symptom Score (mTLSS)	
 Percent change from baseline in hand mTLSS at Week 16
Secondary	Efficacy endpoints:
To evaluate the efficacy of ASN002 in subjects with moderate to severe CHE.	
 Change from baseline in hand mTLSS at Weeks 4, 8, 12, 16 Percent change from baseline in hand mTLSS at Weeks 4, 8, and 12 Proportion of subjects achieving at least a 2-grade reduction from baseline to clear (0), almost clear (1) or mild (2) in hand PGA at Weeks 4, 8, 12 and 16 Proportion of subjects achieving a hand PGA of clear (0) or almost clear (1) at Weeks 4, 8, 12 and 16 Change from baseline in hand PGA at Weeks 4, 8, 12 and 16

PPD	STATISTICAL ANALYSIS PLAN, Version Final 1.0
Protocol Number: ASN002AD-202 V6.0	Sponsor: Asana BioSciences, LLC

OBJECTIVES	ENDPOINTS
	
 • Change and percent change from baseline in Hand Eczema Severity Index (HECSI) at Weeks 4, 8, 12 and 16 • Time to response relative to baseline (based on hand PGA) • Actual hand Patient Global Assessment (PaGA) at Weeks 4, 8, 12 and 16 • Change from baseline in hand Dermatology Life Quality Index (DLQI) at Weeks 2, 4, 8, 12 and 16 • Change and percent change from baseline in pain visual analog scale (VAS) at Weeks 4, 8, 12 and 16
	Safety endpoints:
To evaluate the safety and tolerability of ASN002 in subjects with moderate to severe CHE	
 • Number of Treatment Emergent Adverse Events (TEAEs) • Number of drug-related TEAEs • Proportion of subjects withdrawing for worsening of their CHE at Weeks 4, 8, 12, and 16 • Changes from baseline in vital signs • Change from baseline in ECG • Change from baseline in safety laboratory tests
	Pharmacokinetic endpoints:
To quantify the plasma concentrations of ASN002 in subjects with moderate to severe CHE	
 • Measurement of plasma concentrations of ASN002 in all subjects receiving ASN002 treatment.
Exploratory	Exploratory endpoints:
To evaluate pharmacodynamic (PD), biomarkers and skin microbiome analysis for evidence of drug activity in subjects with moderate to severe CHE	
 • Change from baseline in PD, biomarkers and skin microbiome analysis at Weeks 4 and 16.

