3.4 Randomization, Replacement, and Unblinding Procedures

Subjects will be randomized in a 1:1:1 ratio to one of the following treatment regimens:

- Part A: ASN002 40 mg (16-week treatment); Part B: ASN002 40 mg (16-week treatment)
- Part A: ASN002 80 mg (16-week treatment); Part B: ASN002 80 mg (16-week treatment)
- Part A: Placebo (16-week treatment); Part B: ASN002 80 mg (16-week treatment)

Subjects assigned to regimen starting with a placebo in Part A (first 16 weeks) of the study will receive the highest dose of ASN002 (i.e. 80 mg) for the rest of the treatment period (up to Week 32). Subjects who were assigned to ASN002 in the first part of the study will continue on the assigned treatment dose during the second part of the study up 32 weeks of treatment.

Randomization will occur prior to first dosing, at Day 1 visit. The randomization list will be generated using validated software. Randomization will be stratified for the biopsy collection and for the PGA score of '3' (moderate) or '4' (severe) per treatment group. The master randomization list will be kept secured until the study blind is broken. This list will be uploaded into an Interactive Web Response System (IWRS). The investigator or designee will be able to acquire a randomization number for eligible subjects by connecting to the IWRS

This study will be double-blinded. At all times, treatment and randomization information will be kept confidential and will not be released to, the contract research organization (CRO), or the sponsor's study team until database lock of Part A is completed and all safety data has been cleaned and monitored. Investigators, subjects and clinical staff will remain blinded throughout the study.

PPD	STATISTICAL ANALYSIS PLAN, Version Final 1.0
Protocol Number: ASN002AD-202 V6.0	Sponsor: Asana BioSciences, LLC

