3.5 Changes to the Analysis from the Protocol

Summary of physical examination will not be presented as specified in sections 8.4.2 and 8.4.3 of the protocol as results are not collected unless they appeared as Clinical significance, in which case they are entered as an AE.

Percent change from baseline in hand PGA and foot PGA at Weeks 4, 8, 12, 16, and 32 will not be present as specified in section 3 of the protocol.

PPD	STATISTICAL ANALYSIS PLAN, Version Final 1.0
Protocol Number: ASN002AD-202 V6.0	Sponsor: Asana BioSciences, LLC

Subgroup analysis by PGA strata at baseline (3 vs. 4) will be performed on the primary endpoint (percent change in mTLSS) and key secondary endpoint (proportion with reduction in PGA) as specified in sections 13.1 and 13.2.

Subgroup analysis by baseline description of CHE (hyperkeratotic, fingertip or pompholyx) will be performed on the primary endpoint (percent change in mTLSS) and key secondary endpoint (proportion with reduction in PGA) as specified in section 13.3 for exploratory purpose.

Validated Investigator Global Assessment (for subjects with AD only) will be analyzed as specified in Section 13.3 for exploratory purpose.

The pruritus score portion of the mTLSS will also be analyzed for exploratory purposes as described in Section 13.3.

All secondary efficacy endpoints will be up to Week 16 (Part A). All secondary efficacy endpoints data after week 16 (after the Placebo patients have crossed over to ASN002) will be considered exploratory efficacy endpoints and will be presented using descriptive statistics.

All exploratory efficacy endpoints specified in section 3 of the protocol, will be summarized by all visits with assessment scheduled from Weeks 4 to Week 32 as specified in section 13.3, instead at Weeks 4, 8, 12, 16, and 32.

In section 9.3.2 of the protocol, Holm's step-down procedure adjustment was proposed to adjust for the two comparisons of interest (40mg vs. Placebo and 80mg vs. Placebo). It is well known that the Hochberg method is optimal than Holm's adjustment. Therefore, Hochberg adjustment will be used for the multiple dose/treatment comparisons. The decision for this changed was made before the unblinding. Since this change would not affect the conduct of the trial in any sense, no protocol amendment was made to account for this change.

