6.3 Interim Analysis and Data Monitoring

No Interim analysis has been planned for this study.

PPD	STATISTICAL ANALYSIS PLAN, Version Final 1.0
Protocol Number: ASN002AD-202 V6.0	Sponsor: Asana BioSciences, LLC

The final analyses on efficacy parameters will be done once all patients have finalized their week 16 assessments. All data will be cleaned up to week 16, a database lock of Part A will be performed and final efficacy results will be provided. The efficacy summaries will be updated for additional visits once the Part-B visits are completed; these Part B summaries will be considered exploratory.

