6.7 Analysis Presentation

Subjects will be presented in columns according to their treatment assignment in Part A. In the tables presenting Part B data or combined Part A and Part B data, placebo subjects from Part A

PPD	STATISTICAL ANALYSIS PLAN, Version Final 1.0
Protocol Number: ASN002AD-202 V6.0	Sponsor: Asana BioSciences, LLC

crossed over to ASN002 80 mg will be presented in the placebo/ASN002 80mg column. See Appendix 1 for presentation of treatment groups.

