Dermatology Life Quality Index Questionnaire (DLQI) is a simple 10-question validated questionnaire that has been used in more than 40 different skin conditions. The DLQI is the most frequently used instrument in studies of randomized controlled trials in dermatology. The DLQI total score is defined as the sum of the 10 item scales, ranging from 0 to 30. If missing answers or mistakes, the following rules will be followed:

1. If one question is left unanswered this is scored 0 and the scores are summed and expressed as usual out of a maximum of 30.
2. If two or more questions are left unanswered the questionnaire is not scored.
3. If question 7 is answered 'yes' this is scored 3 even if in the same question one of the other boxes is ticked.
4. If question 7 is answered 'no' or 'not relevant' but then either 'a lot' or 'a little' is ticked this is then scored 2 or 1. If it is answered 'no', but the second half is left incomplete, the score will remain 0.

DLQI will be analyzed as follows:

- Change from baseline in hand Dermatology Life Quality Index (DLQI) at Weeks 2, 4, 8, 12, and 16.

Pain visual analog scale (VAS)

Pain intensity of the CHE will be recorded at the visits specified in Table 1 using a pain Visual Analog Scale (VAS). Pain intensity will be evaluated by asking subjects to place a line perpendicular to the VAS line at the point that represents their worst pain intensity over the last 24 hours.¹³ The pain VAS, represented in Figure 2 is a scale from 0 to 10, where 0 indicates no pain and 10 indicate the worst imaginable pain.¹³

Figure 2: Pain Visual Analog Scale

Pain VAS will be analyzed as follows:

PPD	STATISTICAL ANALYSIS PLAN, Version Final 1.0
Protocol Number: ASN002AD-202 V6.0	Sponsor: Asana BioSciences, LLC

- Change and percent change from baseline in pain visual analog scale (VAS) at Weeks 4, 8, 12 and 16.

Secondary Endpoint Analyses

The key secondary analysis will be based on the data from Part A with the exception of Time to PGA response analysis. MMRM as described for the primary efficacy analyses (Section 13.1) will be used to analyze the change and/or percent change in hand mTLSS, HECSI, DLQI and pain VAS for weeks 4, 8, 12 and 16 (Part A). Analyses will be based on the mITT population and supported by the PP population.

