For categorical efficacy endpoints involving proportions hand PGA, a Cochran Mantel Hansel test (CMH) stratified by baseline PGA will be presented by visit for Part A. Analyses will be based on the mITT population for all secondary parameters and supported by the PP population. Missing data at any post-baseline assessment will be imputed as a non-responder.

Actual values of PaGA will summarized descriptively using frequency and percentage.

Time to response relative to baseline (based on hand PGA) will be compared between treatments using the Kaplan Meier method. A subject will be considered censored if he has not met the event of interest at the end of the study or if the subject is lost to follow up at last observation. Those subjects will be censored at their last available hand PGA assessment.

Descriptive statistics will be presented for all secondary endpoints by visit and treatment group and sorted by Part A.

All endpoints relative Part B for the above assessments are considered exploratory only and will be summarized descriptively by initial treatment group and overall.

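### Time to hand PGA response runs past the Week 16 switch, so responses on ASN002 80 mg count as events in the placebo-randomized arm

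*SAP*

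**What the plan says.** SAP 13.2, under Secondary Endpoint Analyses, singles out one analysis: "The key secondary analysis will be based on the data from Part A with the exception of Time to PGA response analysis". Response is a hand PGA of 0 or 1. On censoring, the same section says "A subject will be considered censored if he has not met the event of interest at the end of the study", adds loss to follow-up, and places the censoring time at the last available hand PGA. Treatments are to be compared with the Kaplan-Meier method; no test is named.

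SAP 3.4 gives the third regimen as "Part A: Placebo (16-week treatment); Part B: ASN002 80 mg (16-week treatment". The mITT population is analyzed as randomized (SAP 4.1). SAP 6.7 says placebo subjects "crossed over to ASN002 80 mg will be presented in the placebo/ASN002 80mg column" in tables that include Part B.

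Three other statements point the opposite way:

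- SAP 3.5: "All secondary efficacy endpoints will be up to Week 16 (Part A"; later data are exploratory and descriptive, and the reason given is that placebo patients have by then crossed over.
- SAP 6.3: final efficacy analyses follow completion of Week 16, and for the later update "these Part B summaries will be considered exploratory".
- SAP 13.2, closing line: "All endpoints relative Part B for the above assessments are considered exploratory only".

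SAP Section 2 does not settle the matter. It lists "Time to response relative to baseline (based on hand PGA" as a secondary endpoint with no week limit, and its list of Part B exploratory endpoints omits it.

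**The concern.** A comparison of ASN002 with placebo needs the placebo arm to be on placebo for the whole period compared. Here the period appears to run to the end of the study, while the placebo arm is on placebo only to Week 16. After that, the placebo-randomized curve describes a delayed start of 80 mg, and any contrast with it is immediate versus delayed start. The SAP does not say so.

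At stake are the separation of the curves after Week 16, any between-arm contrast of medians reached after Week 16, and any whole-curve test or hazard ratio. The usual direction is dilution toward no difference. The 40 mg comparison is affected too, because placebo-randomized subjects are then on the higher of the two doses.

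There is also a practical problem. A programmer following 13.2 and one following 3.5 would produce different analyses of the same endpoint.

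**Working it through.** **1. Which events count.** The event is the first hand PGA of 0 or 1, with no week limit. Hand PGA is scheduled at Weeks 2, 4, 8, 12, 16, 20, 24, 28, 32 and the follow-up visit (Protocol 1.3, Table 1). Nothing in 13.2 censors at Week 16 or at the switch. Subjects stay in their randomized arm. A placebo-randomized subject who first reaches 0 or 1 at, say, Week 24 on 80 mg is therefore an event in that arm. No single sentence states this; it follows from the exception, the censoring rule and the as-randomized analysis together. Week 16 assessments precede dosing (Protocol 1.3), so Kaplan-Meier estimates up to and including Week 16 are clean.

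**2. The plan's own figures.** None exists for this endpoint. SAP 5.1 sizes the primary endpoint: SD 39, differences of 25 and 35 points, general F test, 25 per group. That reproduces (82.5% power at 25 per group; 24 gives 80.8%). It has no bearing here beyond supplying 35 per arm and 25-30% dropout.

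**3. Closed form.** Assume constant hazards, with crossovers taking on the 80 mg hazard at Week 16. Let p and a be the Week 16 response probabilities on placebo and 80 mg.

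- Week 16 gap: a − p.
- Week 32, placebo-randomized: 1 − (1−p)(1−a).
- Week 32, 80 mg: 1 − (1−a)².
- Week 32 gap: (1−p)(1−a) − (1−a)² = (1−a)(a−p).

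The gap therefore shrinks by the fraction a, that is by 30-50% for a between 30% and 50%. With p = 0.10 and a = 0.35:

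- Week 16: 35 − 10 = 25 points.
- Week 32: placebo-randomized 1 − 0.90 × 0.65 = 41.5%; 80 mg 1 − 0.65² = 57.75%; gap 0.65 × 25 = 16.25 points.
- Share of placebo-arm events after the switch, before dropout: 0.90 × 0.35 / 0.415 = 76%.

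**4. Simulation with dropout.** Same hazards, response read at the scheduled visits to Week 32, 35 per arm, 27.5% exponential dropout per 16 weeks (midpoint of the planned range), censoring at the last attended visit, two-sided 5% log-rank test, 20,000 replicates per pair (Monte Carlo SE at most 0.4 points).

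| Assumed Week 16 response, placebo / 80 mg | Power, cut at Week 16 | Power, to Week 32 | Placebo-arm events after switch |
|---|---|---|---|
| 5% / 30% | 75% | 44% | 80% |
| 5% / 50% | 99% | 83% | 88% |
| 10% / 30% | 49% | 29% | 66% |
| 10% / 35% | 65% | 40% | 70% |
| 10% / 50% | 94% | 74% | 77% |
| 15% / 40% | 59% | 38% | 62% |
| 20% / 30% | 14% | 11% | 46% |
| 20% / 50% | 70% | 49% | 59% |

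At 10% / 35%, about 6.6 of 9.5 placebo-arm events fall after the switch. Over all 16 pairs of placebo 5, 10, 15, 20% with active 30, 35, 40, 50%, power falls in every pair and the post-switch share is 46-88%. Using 25% or 30% dropout moves the 10% / 35% result by at most 1 point.

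**5. Sensitivity to the constant hazard.** If the response hazard in the 80 mg arm halves after Week 16 while crossovers start at the full hazard, the loss is larger. Without dropout, at 10% / 35% and 35 per arm, Week 32 power is 16% instead of 40%.

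**The case against.** The strongest reply is that the passages can be harmonized. SAP 6.3 provides for a final analysis at the Part A lock and an exploratory update afterwards. The exception in 13.2 might mean only that the Kaplan-Meier display continues past Week 16. Subjects randomized to ASN002 stay on their dose, so their later estimates and medians are valid for that regimen, and wanting a median when fewer than half respond by Week 16 is a sensible reason to extend follow-up. The combined column label discloses the switch, and SAP Appendix 1 anchors the two 80 mg groups by first dose in combined outputs. No test is named, so the power figures are hypothetical. The dilution would rarely create a false claim, and the p-values are nominal.

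Some of this stands. The active-arm curves can be read on their own, the conflict with 6.3 is one of timing and status, and the power figures are illustrative. The main point survives. SAP 3.5 has no exception, and 13.2 compares treatments with follow-up to the end of the study. A label does not remove events or move a censoring date. The Appendix 1 anchoring is written for displays by treatment and visit, and 13.2 does not apply it to time to response. The shrinking gap needs no test to appear.

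**Conclusion.** The concern holds. As written, 13.2 gives a between-arm comparison in which the placebo-randomized arm accrues events on ASN002 80 mg, against SAP 3.5 directly and against the exploratory status of Part B in 6.3 and in 13.2 itself.

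That conclusion rests on the text alone. Its size rests on assumed response rates, constant hazards and crossovers taking on the active hazard at once. The model stops at Week 32 although hand PGA is also scheduled at follow-up, and it does not set data after prohibited medication to missing (SAP 6.2). The power figures further assume a log-rank test.

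The reach is limited to one secondary endpoint without multiplicity adjustment (SAP 6.5). The primary MMRM and the PGA responder tests are unaffected. It should be fixed before the analysis is run, but it does not threaten the trial's main conclusion.

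**What to change.** - In SAP 13.2, delete the clause that excepts time to PGA response from the Part A limit.
- For the between-arm comparison, censor every subject without a response at the last hand PGA on or before the Week 16 pre-dose assessment, and name the test or summary to be used.
- Present Part B time to response descriptively only, under the combined placebo/80 mg label and timed from the first ASN002 dose for crossovers. Add it to the Part B exploratory list in SAP Section 2, and put the Week 16 limit on the secondary endpoint there.

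The cost is a few lines of SAP text and a different censoring date in one program. No new data are needed.

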3 STUDY DESIGN

3.1 Overall Design

This study will be performed at approximately 20-25 study centers located in the United States and Canada.

Approximately 105 subjects with moderate to severe CHE (as defined by a hand PGA = 3 or 4 at Day 1) will be included in this randomized, double-blind, placebo-controlled, multicenter, Phase 2 study. Subjects will be men or women, 18 years of age or older, at the time of consent. Subjects with moderate CHE will be limited to 30% of total enrollment.

Each subject should read and sign an informed consent form prior to any screening procedures being performed. Subjects who fulfill all of the inclusion criteria and none of the exclusion criteria will be accepted into the study. After a screening period of no more than 30 days (from Day -30

PPD	STATISTICAL ANALYSIS PLAN, Version Final 1.0
Protocol Number: ASN002AD-202 V6.0	Sponsor: Asana BioSciences, LLC

to Day -1), eligible subjects will be randomized (1:1:1) on Day 1 to receive ASN002 at 40 mg or 80 mg, or placebo once daily for 16 weeks (Part A). Randomization will be stratified for the biopsy collection and for the PGA score of '3' (moderate) or '4' (severe) per treatment group. Then, in Part B, subjects who were assigned to placebo in the first part of the study will receive the highest dose of ASN002 (i.e. 80 mg) for the rest of the treatment period (up to Week 32). The subjects who were assigned ASN002 in the first part of the study will continue on the same assigned treatment dose during the second part of the study (Week 16 to Week 32). The total treatment period of 32 weeks will be followed by a 4-week follow-up period. For scheduled study visits, subjects will come to the study centers on 13 occasions: screening; Day 1; Weeks 2, 4, 8, 12, 16, 18, 20, 24, 28 and 32 (end of treatment visit); and Week 36 (follow-up visit)/early termination (ET).

[figure not shown]
Efficacy will be assessed using mTLSS, PGA, HECSI, pain VAS and Extent of Disease. In addition, a 6-grade PaGA scale will be used. Quality of life will be evaluated using DLQI. Impact on work productivity and activity will be studied using the WPAI-SHP questionnaire.

Safety will be assessed by collecting AEs, recording vital signs, performing physical examination and 12-lead ECG, and evaluating clinical laboratory tests.

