- Change from baseline in hand PGA at Weeks 4, 8, 12 and 16.
- Time to response defined as achieving an assessment of clear (0), or almost clear (1) in hand PGA.

Subgroup analysis by PGA strata at baseline (3 vs 4) will be done on the following endpoints:

- Proportion of subjects achieving a hand PGA of clear (0) or almost clear (1) at Weeks 4, 8, 12 and 16.
- Proportion of subjects achieving at least a 2-grade reduction from baseline to clear (0), almost clear (1) or mild (2) in hand PGA at Weeks 4, 8, 12 and 16.
- Change from baseline in hand PGA at Weeks 4, 8, 12 and 16.

Hand Eczema Severity Index (HECSI)

The HECSI scoring system incorporates both the extent and the intensity of the disease. Each hand will be divided into five areas [fingertips, fingers (except the tips), palms, back of hands and wrists]. For each of these areas the intensity of the six following clinical signs: erythema, induration / papulation, vesicles, fissuring, scaling and oedema will be graded on the following scale: 0, no skin changes; 1, mild disease; 2, moderate and 3, severe. For each location (total of both hands) the affected area will be given a score from 0 to 4 (0, 0%; 1, 1–25%; 2, 26–50%; 3, 51–75% and 4, 76–100%) for the extent of clinical symptoms. Finally, the score given for the extent at each location will be multiplied by the total sum of the intensity of each clinical feature, and the total sum called the HECSI score will be calculated, varying from 0 to a maximum severity score of 360 points. The score will be set to missing in case of at least one missing value.

A detailed description of the HECSI scoring system is shown in

HECSI will be analyzed as follows:

- Change and percent change from baseline in Hand Eczema Severity Index (HECSI) at Weeks 4, 8, 12 and 16.

PPD	STATISTICAL ANALYSIS PLAN, Version Final 1.0
Protocol Number: ASN002AD-202 V6.0	Sponsor: Asana BioSciences, LLC

Table 4.

HECSI will be analyzed as follows:

- Change and percent change from baseline in Hand Eczema Severity Index (HECSI) at Weeks 4, 8, 12 and 16.

Table 4. Hand Eczema Severity Index

Clinical Signs	Fingertips	Fingers (except tips)	Palm of Hands	Back of Hands	Wrists
Erythema (E)					
Infiltration / Papulation (I)					
Vesicles (V)					
Fissures (F)					
Scaling (S)					
Oedema (O)					
SUM (E + I + V + F + S + O)					
Extent (Ex)					
Total HECSI score =	Sum xEx +	Sum xEx +	Sum xEx +	Sum xEx +	Sum xEx

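### SAP 13.2 names neither a test nor a stratum for time to hand PGA response; a log-rank test stratified by baseline PGA would close the gap at almost no cost

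*SAP*

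**What the plan says.** SAP 13.2 defines the endpoint as "Time to response defined as achieving an assessment of clear (0), or almost clear (1) in hand PGA". Under Secondary Endpoint Analyses it says: "Time to response relative to baseline (based on hand PGA) will be compared between treatments using the Kaplan Meier method". A censoring rule follows: "Those subjects will be censored at their last available hand PGA assessment". No log-rank test, Cox model, hazard ratio or stratum is given.

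The preceding part of the same section handles the binary PGA responses differently: "a Cochran Mantel Hansel test (CMH) stratified by baseline PGA will be presented by visit for Part A". SAP 3.4 says of allocation: "Randomization will be stratified for the biopsy collection and for the PGA score of '3' (moderate) or '4' (severe) per treatment group". SAP 3.1 adds: "Subjects with moderate CHE will be limited to 30% of total enrollment".

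Nothing elsewhere fills the gap. SAP 6.1 covers covariates for continuous efficacy parameters only. Protocol 9.3.2 covers continuous and categorical endpoints only. SAP 5.6 sets two-sided tests at 0.05, and SAP 6.5 expects nominal p-values for secondary endpoints.

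**The concern.** There are two gaps in one sentence.

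First, Kaplan-Meier is an estimator. The SAP promises a comparison, and SAP 6.5 anticipates a p-value, but the procedure that would produce it is open. Log-rank, Wilcoxon and Cox tests, stratified or not, can give different answers on the same data. The sponsor and CRO are unblinded after the Part A lock (SAP 3.4), so it is better to fix the choice before then.

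Second, baseline PGA bears directly on this endpoint. To reach PGA 1, a subject who enters at 3 must fall 2 grades and one who enters at 4 must fall 3. If that makes response slower in the severe stratum, an analysis that pools the strata loses some power. The factor is already in the randomisation and in the CMH test of the same response, so using it here needs no new data.

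**Working it through.** **The plan's own figure.** The documents give no power figure for time to response. The only sample-size statement (SAP 5.1) concerns the primary endpoint. With group means 0, 25 and 35 (overall mean 20) and SD 39, the noncentrality at n = 25 is 25 × (20² + 5² + 15²)/39² = 25 × 650/1521 = 10.7. The F test then has 82.5% power, and the smallest n reaching 80% is 24 (80.8%). Dropout: 25/0.75 = 33.3 and 25/0.70 = 35.7, consistent with 35 per group. The figure reproduces, but it does not bear on this point.

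**Inputs from the documents.** 35 per arm; a ceiling of 30% moderate subjects; 25-30% dropout; PGA visits at Weeks 2, 4, 8, 12 and 16; two-sided 5%.

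**Assumptions not in the documents.** Placebo response by Week 16 in the PGA 4 stratum of p = 10% or 20%; treatment hazard ratio 2.5 to 3.5; hazard ratio for response, PGA 3 against PGA 4, of 1 to 4; moderate share 15% or 30%.

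**Method.** Response times are exponential with severe-stratum placebo hazard −ln(1 − p)/16 per week, multiplied by the PGA and treatment hazard ratios and read only at scheduled visits. The implied placebo response in moderate subjects is 1 − (1 − p)^HR. For p = 10% that is 19%, 27% and 34% at PGA hazard ratios 2, 3 and 4; for p = 20% it is 36%, 49% and 59%. Both log-rank tests, unstratified and stratified by PGA, were applied to the same simulated trials.

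**Results to Week 16**, 80 mg against placebo, treatment hazard ratio 3, 4000 runs each (power in %, gain in points, taken before rounding):

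| Moderate share | PGA HR | p | Unstratified | Stratified | Gain |
|---|---|---|---|---|---|
| 30% | 2 | 10% | 46.1 | 46.8 | 0.7 |
| 30% | 2 | 20% | 71.1 | 72.2 | 1.1 |
| 30% | 3 | 10% | 49.9 | 52.8 | 2.9 |
| 30% | 3 | 20% | 72.6 | 76.8 | 4.2 |
| 30% | 4 | 10% | 50.8 | 56.8 | 5.9 |
| 30% | 4 | 20% | 70.3 | 79.3 | 9.0 |
| 15% | 2 | 10% | 41.9 | 42.8 | 0.8 |
| 15% | 2 | 20% | 68.5 | 68.6 | 0.1 |
| 15% | 3 | 10% | 43.4 | 45.4 | 1.9 |
| 15% | 3 | 20% | 67.5 | 69.7 | 2.1 |
| 15% | 4 | 10% | 45.2 | 48.8 | 3.7 |
| 15% | 4 | 20% | 68.6 | 73.8 | 5.1 |

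With treatment hazard ratios 2.5 and 3.5 and 30% moderate, the gains are 0.6 to 1.3 points at PGA hazard ratio 2 and 5.7 to 9.8 at 4. At 1 the change is −0.6 to −0.1 (for example 46.9% to 46.5%), so stratifying costs practically nothing.

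**Type I error.** With no treatment effect and PGA hazard ratio 4, the unstratified test rejected 3.7% and 4.1% of the time to Week 16, and the stratified test 4.4% and 5.9%. The unstratified test is therefore mildly conservative, and part of the gain at 4 reflects that.

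**Second set of scenarios** (5000 runs, about 30% moderate, 28% dropout), specified by Week 16 response in severe/moderate subjects. The implied PGA hazard ratio is ln(1 − p_moderate)/ln(1 − p_severe).

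| Placebo | Active | Implied PGA HR, placebo; active | Unstratified | Stratified |
|---|---|---|---|---|
| 10/30% | 35/60% | 3.4; 2.1 | 61.5 | 62.7 |
| 5/40% | 30/75% | 10.0; 3.9 | 69.1 | 74.3 |
| 10/50% | 35/85% | 6.6; 4.4 | 64.7 | 73.0 |
| PGA not prognostic | | 1; 1 | 63.5 | 63.0 |

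Here too, gains above about 1 point appear only when PGA is strongly prognostic.

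**The case against.** The best defence is that this is a small omission and that the loss of power is conjectural. Most of that stands.

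- A reader might infer that the SAP prescribes an unstratified test. It does not; it is silent. Unstratified is the natural reading beside a CMH test with an explicit stratum, but it remains an inference. With no test named, strictly no planned power is being given away.
- A reader might infer a material loss of power. No response rate by PGA stratum appears in the documents, and 30% is a ceiling on moderate subjects, not an expectation. Gains of 5 points or more need a PGA hazard ratio of about 4 or higher.
- A reader might infer that the result would be inconsistent with the CMH analysis. The two already differ by design: CMH works visit by visit and counts missing as non-response, while time to response censors. Unstratified curves are also valid under randomisation, and pooling the strata did not inflate false positives.
- Stratification is not treated as mandatory elsewhere. The primary MMRM includes PGA only if it is not highly correlated with baseline mTLSS, and SAP 13.2 already gives PGA 3 and 4 subgroup results for the binary response.

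What the defence does not answer is that a between-group comparison is promised with no method that can deliver it.

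**Conclusion.** The point holds as a specification gap with a nearly free improvement. SAP 13.2 should name a test, an effect measure and the stratum for time to hand PGA response.

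The benefit of stratifying, under the assumed response rates and Week 16 follow-up, is roughly 0 to 4 points of power for a PGA hazard ratio of 1 to 3. It is 6 to 10 points only if that ratio is about 4 with 30% moderate subjects, and less with fewer. This is one secondary endpoint with nominal p-values, so the primary conclusion, the sample size and the safety analysis are untouched.

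Follow-up is a separate matter. SAP 13.2 says "The key secondary analysis will be based on the data from Part A with the exception of Time to PGA response analysis", and its censoring rule refers to the end of the study. The same section closes by making Part B endpoints exploratory and descriptive, and SAP 3.5 ends all secondary efficacy endpoints at Week 16. These statements need reconciling, because placebo subjects receive ASN002 from Week 16. In the simulation with treatment hazard ratio 3 and 30% moderate, extending follow-up to Week 32 with that switch lowered unstratified power from 46-73% to 27-53%. That is usually more than stratification recovers, but adding a stratum neither causes nor cures it.

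**What to change.** In SAP 13.2, Secondary Endpoint Analyses, replace the Kaplan-Meier sentence with a specification that:

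- compares each dose with placebo by a two-sided log-rank test stratified by baseline hand PGA (3 or 4), with a nominal p-value;
- reports a Cox hazard ratio stratified the same way, with its 95% CI;
- states how ties are handled, since responses can be recorded only at scheduled visits and many will share a time;
- keeps the Kaplan-Meier curves as display, overall and by PGA stratum.

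Using PGA alone, without the biopsy factor, matches the MMRM and CMH analyses.

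The cost is a few lines of SAP text and a strata statement in the program. No data, visits or subjects are added. Protocol 9.3.2 prescribes no time-to-event method, so nothing there is contradicted. The text should be settled before the Part A unblinding.

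Separately, reconcile the statements in SAP 13.2 and 3.5 on whether this comparison ends at Week 16. Limiting it to Part A would change the planned follow-up and should be recorded as its own decision.
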